Patient flow from the time of initial diagnostic studies, to actual diagnosis and to treatment differs at every site. We are experienced with these patterns and can incorporate recruitment strategies into the clinical flow of care. The UNC patients are all processed through a central site, the Multi-disciplinary Thoracic Oncology Program (MTOP). Note that a patient list is available the Friday prior to MTOP clinic. This list includes patients' names, the description of his or her lung lesion, diagnosis, cancer stage (if determined), and whether the appointment is an initial appointment or follow-up visit. The RA and site PI will identify patients, in advance, who are most likely to be study candidates. The appropriate clinicians will be approached at the beginning of MTOP to confirm the patient's study eligibility and to obtain permission to approach the patient. As MTOP only meets one day a week and in a single location, a research assistant will spend every Tuesday at the MTOP site and work with staff to identify specific patients that meet inclusion criteria, obtain informed consent, and arrange a time for completion of the patient questionnaire. The RA will administer all questionnaires orally, and all participating patients will be paid \$30 at completion. Patients will also receive \$10 for each completed follow-up interview (6 months then 12 months after enrollment). At ECU, the format is identical except about one-fifth of lung cancer patients enter the system through a standard pulmonary clinic. The review of the patient list, the confirmation of eligibility, and enrollment process at ECU will proceed exactly as per the description at UNC. Lung cancer care in Greensboro has been decentralized in the past. However, the regional cancer center has recruited a lung cancer navigator and established a formal MTOP structure. All lung cancer providers (thoracic surgeons, pulmonologists, oncologists, and radiation oncologists) have agreed to refer potential and diagnosed lung cancer patients for case discussion to the program clinic prior to surgical or other treatment decisions and will utilize a multidisciplinary and multi-specialty decision-making format. Patients will now be accessible at a common site before treatment decisions are finalized. The MTOP clinic roster will be available to the RA and site PI 48 hours in advance and the patient identification and enrollment process will proceed as described at ECU and UNC.

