USC also has an MTOP conference but about one-third of patients are discussed after therapy has been determined by the referring physician. However, the pulmonary division has established a solitary pulmonary nodule clinic specifically designed to identify patients with early stage lung cancer who then rapidly progress to diagnostic evaluation and treatment recommendations. There are 2 clinic sessions per month and 15 patients evaluated in each clinic. The USC site investigator and RA will have access to the nodule clinic schedule and determine potential patient eligibility prior to clinic. As with the MTOP clinics above, the RA will attend the nodule clinic, the appropriate clinicians will be approached to confirm patient's study eligibility and to obtain permission to approach the patient. We will also intensify recruitment at thoracic surgery offices in an effort to capture the patients treated prior to MTOP and not seen in solitary nodule clinic. Note that none of the participating sites use formal communication protocols that define minimum information delivery or ascertainment of patient comprehension.

All 4 study sites are referral centers for lung cancer treatment with large catchment areas. We surveyed the lung cancer physicians and coordinators at all 4 centers regarding a potential diffusion effect between study patients and controls. Because of widespread geographic distribution of patients and MTOP scheduling sequences during visits the possibility of intervention and control patients meeting and discussing variations in communication is remote. To further ensure against a diffusion effect, we will alternate control and intervention recruitment dates as part of the randomization scheme.

In our cohort study, 80% of the patients enrolled identified a pulmonologist, thoracic surgeon, or oncologist as the individual who told them the most about lung cancer. These specialists

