Given the continued late stage of lung cancer presentation, particularly among African-Americans [3], we will continue our multi-pronged recruitment approach to find as many patients with early stage, non-small cell cancer as we possibly can. In addition to the electronic CT search, we will continue to engage specialists who see those patients with lung cancer that are indeed referred. Pulmonologists and thoracic surgeons care for the largest concentration of non-small cell lung cancer patients. We'll focus our physician office recruiting efforts on these specialties. As we did with our first prospective study, we will give participating physicians and their office liaisons a project summary sheet that will include the telephone number and beeper number of the PI and research assistant (RA). We will ask that all patients who have the probable diagnosis of resectable lung cancer be referred. We will advise practices that we are responsible for confirming inclusion criteria and obtaining informed consent. In addition, we will provide participating offices information sheets to give to potential enrollees. These documents will describe the study and contain clear statements emphasizing that patient care would not be compromised should individuals decide against participating. For patients who express interest, the office liaison will record the patient's name and telephone number. We will contact each office on at least a weekly basis to remind the staff of the study and to obtain the information on potential enrollees. We will telephone patients to further explain the study and arrange a meeting to obtain informed consent and proceed with the interview.

Patients with lung cancer represent an extremely small proportion of primary care and resident physician practice panels. However, we will not eliminate these practices from consideration. We will attend primary care staff meetings and residency morning reports on a regular basis to remind these physicians of the study. Traditionally, oncologists have been consulted for patients who have advanced disease. With the growing emphasis on adjuvant chemotherapy for early stage lung cancer, these specialists are much more likely to encounter potential study patients. We will therefore regularly attend thoracic oncology conferences and remind oncology physicians, including radiation oncologists of our study.

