Given the ratio of catchment area patients that receive their lung cancer care at each study site and a conservative, estimated an overall recruitment rate of 50%, we will be able to recruit 165 stage I and II patients per year combining all study sites. We anticipate 3 yrs of patient recruitment with the accrual of 496 patients. We will oversample black patients, as we did in our prospective study, to attain an enrollment goal of 30%.

3. The Interview and Survey Instruments

Patient Interview. We will administer the surveys as face-to-face interviews, conducted by

thoroughly trained RAs at each site. We will attempt to arrange interviews at the convenience of the patient. Before the project begins we will give all RAs a script and provide rigorous training in its use so that interview technique and content will be consistent at all sites; we will also develop and provide training manuals. We will interview patient-participants in private settings. For onsite interviews, we will identify rooms in the same building or adjacent buildings that are apart from clinic. Offsite interview venues will include the investigator's institution, the patients' homes, or other mutually agreeable locations. All interview sites will be private and secure. If patients require more than one sitting to complete the survey because of fatigue or time constraints, we will accommodate such needs.

Patient Questionnaire. The proposed instrument builds on our preliminary work (Appendix E) by formally measuring health literacy. Low literacy likely identifies patients for whom the communication intervention might be more needed and effective. The questionnaire also covers the following constructs and relies on reliable and validated items or batteries drawn from previous instruments. Specifically areas included will be:

1. *Demographic Information:* age, sex (recorded only by interviewers, not asked), marital status, race, educational attainment, estimated household income, type of health insurance, access to a regular source of care, and affiliation with any church or denomination.
2. *Health Status:* Physicians may use poor physical or emotional function as a contraindication for cancer surgery; patients may opt against surgery because of poor health-related quality of life. We will use the SF-12 [23], to assess this domain. (Appendix C)
3. *Health Literacy:* Test of Functional Health Literacy in Adults-short form [61] (Appendix C)

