4. *Communication Variables:* The attitudes coupled with Likert-type scales that identified perceptions of communication associated with surgical decisions from the initial study.
5. *Trust:* The Medical Mistrust Index [93]

6-month Telephone Interview

1. Health Status: repeat SF-12
2. Communication Variables as above
3. Patient satisfaction cancer care including the choice of treatment

12-month Telephone Interview. Will repeat 6 month items. To fully assess the importance of lung resection surgery within 4 months of diagnosis, we will determine whether each patient, surgical and nonsurgical, remains alive one year. We will re-administer the SF-12 survey and satisfaction measures by telephone to survivors. We will find patients by maintaining a linkage file that includes best telephone number file, stored separately from original survey information. If the patient is not located at the original number, we will seek current information from the office of their physician or through local phone listings. If a patient surrogate answers the phone, we will seek the patient's availability and clinical status in the conversation with the surrogate.

4. *Interventions – Each site will identify a physician leader to serve as a liaison to the CCE.*
 - A. Cancer Communication – Because of the gaps between documented outcomes of lung cancer surgery and patient communication barriers identified in our recent work, our communication intervention will focus on improving presentation of risk information and confirmation of understanding [13]. Given good post operative outcomes [45, 94] in most patients with significant comorbidities, and the doubling of one-year mortality in our prospective “no surgery” group, patients’ perceptions of worse one-year prognosis with surgery are either misinterpreted or poorly explained. In lung cancer only one-half of patients comprehend proposed treatment within 3 days of their clinical visit and only 40% expressed satisfaction with communication [60]. Moreover, effective communication skills, such as active listening and the teach-back method, which can assist education and confirm understanding are used infrequently in clinical care. For example, Schillinger demonstrated that only 12% of new concepts had confirmation (teach back) by the clinician in encounters for diabetes [59]. Several studies have documented difficulty understanding numbers and calculations, particularly the idea of risk [95].

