Presenting risk clearly, with specific formats, and talking through the issues can help to improve patient understanding. Health literacy related oral communication techniques, such as the teach-back method, can help the educator confirm understanding and enhance clinical outcomes [59]. Because of difficulty in communicating risk, and the infrequency of optimal communication strategies in usual care, our experienced investigator team will carefully construct content and nuances of risk communication and training and protocols for educators to use best practices, such as active listening and the teach-back. Our team includes experts in health literacy ([name]) and disparities communication (Drs. [name], [name], and [name]) and we have extensive experience developing successful, culturally sensitive risk communication [96-100, 13]. We will ensure that short term consequences and cure rates are well understood and one year mortality information is clearly described with and without surgery. The communicator will “close the loop” at **multiple points over time** to ensure patient comprehension. If surgical decisions don’t fit prognosis, we will use alternative methods to convey information such as narratives or story telling [101]. As a key component of intervention development, we will test comprehension of our message and acceptability of communication techniques using individual patient interviews prior to the randomization phase. We will use the interviews iteratively to develop the intervention techniques and include people with low health literacy and low numeracy. These interviews will be taped (with consent) for fidelity of factual information and delivery techniques, and the CCE will be given feedback based on the tapes. After the final tools are developed, the CCE will use the lung cancer algorithms and teach-back confirmation with all participants *who are randomized to the CCE intervention. The CCE will have a face to face sessions at initial diagnosis and one 10 to 14 days after diagnosis.* More visits will be scheduled if the CCE cannot confirm patient understanding of risk and prognosis. *The CCE will re-engage any individual who is randomized to the patient intervention and who drops out of care as defined by a lack of follow-up appointment within a month of the index visit, failure to schedule surgery when recommended, or a missed appointment for follow-up or procedures. The CCE will inform the designated site physician champion about direct recommendations against surgery if no absolute contra-indications are defined in the record. The physician champion will arrange clinical evaluations as noted below. Patients in the intervention group will be encouraged to initiate contact with the CCE when questions or concerns occur.*

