The modeling approach will be to initially define as large a maximum model as possible using main effects only (initially no interactions). Preliminary analyses of similar data indicates that the sample size combined with a sufficient number of events (surgery yes) will allow upwards of 30-35 main effects to be included in the model with good reliability for estimation and inference. The generalized estimating equations (GEE) for binary outcomes will be used to fit logistic regression models for clustered data [102]. The primary outcome variable is binary, surgery yes or no, and outcomes of patients clustered within the same site (and/or MD) are expected to be correlated. GEE will allow fitting a logistic regression to the binary outcome while adjusting for the effect of clustering within the same site (and/or MD). As stated previously, independent variables in these analyses will include important demographic variables such as age, race, marital status, household income, health insurance, gender, and education as well as measures of trust, patient satisfaction, functional status, self-reported health, comorbid illness, perceptions of communication, and the communication intervention. The significance of each of the main effects while adjusting for all other effects from the maximum model will be assessed. A backwards elimination approach will, initially, remove effects with a p-value of greater than 0.10. This excludes selected predictors forced predictors into the model (forced predictors include group, comorbid illnesses and selected baseline scores). The reduced model will be refit. Variables have p-values greater than 0.05 will then be removed. The final reduced main effects model, including forced predictors will be refit. Selected interactions will be considered for inclusion into the final reduced main effects model. For the secondary outcomes, survival analysis techniques will be used to assess the one year, post-enrollment survival in surgical and non-surgical groups. Kaplan-Meier curves will be generated. Linear regression models for repeated measures (discrete) outcomes using GEE will be used to assess patient satisfaction of patients that received interventions compared to those who did not, for patients' perceptions of communication for those patients that received intervention compared to those who did not, and for SF12 scores at 6 months post-enrollment and 12 months post enrollment. Covariates will include baseline, group, and other covariates listed above.

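### Nothing requires the enrolment questionnaire to precede the communicator's first session, so scores used as baseline adjusters can carry the intervention's effect in one arm only

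*Protocol*

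**What the plan says.** **Questionnaire timing.** Protocol E.2, describing the UNC clinic, has the research assistant "obtain informed consent, and arrange a time for completion of the patient questionnaire". ECU and Greensboro are said to follow the same enrolment process. E.3 adds "We will attempt to arrange interviews at the convenience of the patient", allows offsite venues, and says "If patients require more than one sitting to complete the survey because of fatigue or time constraints, we will accommodate such needs". For office referrals, E.2 has staff telephone the patient and "arrange a meeting to obtain informed consent and proceed with the interview".

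**Questionnaire content.** E.3 lists the SF-12, a health literacy test, the Medical Mistrust Index, and Likert-type items on "perceptions of communication associated with surgical decisions from the initial study". Satisfaction with care is listed only for the 6- and 12-month telephone interviews.

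**CCE sessions.** E.4.A: "The CCE will have a face to face sessions at initial diagnosis and one 10 to 14 days after diagnosis".

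**Allocation.** E.2: "we will alternate control and intervention recruitment dates as part of the randomization scheme".

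**Use of the scores.** In SAP section 6 (Specific Aim 1), the GEE logistic model for surgery lists trust, patient satisfaction, functional status and perceptions of communication together with the communication intervention. Backward elimination spares some terms: "forced predictors include group, comorbid illnesses and selected baseline scores". The repeated-measures models for satisfaction, communication and SF-12 carry baseline and group as covariates.

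**The concern.** A baseline covariate is safe to adjust for because treatment cannot have changed it. Here the CCE session is scheduled early, the interview has no deadline, and arm is set no later than the consent date. The schedule therefore permits a score to be recorded after the intervention has begun, and only in the intervention arm.

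Communication is the mechanism the trial sets out to change. If the first session has already moved the communication or trust score, adjusting for it removes part of the effect on surgery that the trial is meant to estimate. For perceptions of communication and SF-12 at 6 and 12 months, a shifted starting value in one arm distorts the group difference directly.

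**Working it through.** **1. Order of events, from the text.** Consent comes first at the MTOP clinics, then a time is booked for the questionnaire. Arm follows the recruitment date, so it is set by then. The first CCE session is tied to diagnosis, not to completion of the questionnaire. The only wording about doing something before randomization concerns pretesting of methods and instruments (Protocol E) and interviews used to develop the intervention (E.4.A). No sentence puts the questionnaire before CCE contact on either the clinic or the office-referral route.

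**2. The plan's own figure.** SAP section 7 gives no two-arm power and nothing on this issue. Its Aim 1 figure is a one-sample test with n = 496, 0.63 to 0.69, at 0.05 (two-sided per SAP section 6):

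power = Φ{[(p1 − p0)√n − 1.96√(p0(1 − p0))] / √(p1(1 − p1))} = Φ{[0.06 × 22.27 − 1.96 × 0.4828] / 0.4625} = Φ(0.843) = 0.80.

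The stated 80% reproduces and is not in dispute.

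**3. Illustration for surgery.** All inputs are assumed except the 0.63 and the 496. Let A be arm (1:1) and C the true pre-contact communication score in SD units:

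logit P(surgery) = a + τA + b(C + dA), with total conditional log odds ratio T = τ + bd.

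Here b is the log odds of surgery per SD of score and d is the shift from the first session. The constants give 63% surgery in controls and an assumed 75% in the intervention arm, so T = 0.585 when b = 0.4 and 0.637 when b = 0.8. The recorded baseline equals C, plus d for the share f of intervention patients interviewed after the session. Surgery is then regressed on A and the recorded score.

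At f = 0 the arm coefficient is T. At f = 1 it is T − bd. For b = 0.8 and d = 0.5 that is 0.637 − 0.40 = 0.237, an odds ratio of 1.27 (simulated 1.28). For b = 0.4 and d = 0.2 it is 0.585 − 0.08 = 0.505, an odds ratio of 1.66 (simulated 1.67).

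Adjusted odds ratio (400,000 simulated patients), with power at N = 496 in brackets (1,500 simulated trials, two-sided 0.05):

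| b | d | f = 0 | f = 0.25 | f = 0.5 | f = 1 |
|---|---|---|---|---|---|
| 0.4 | 0.2 | 1.79 (0.845) | 1.76 (0.817) | 1.72 (0.774) | 1.67 (0.721) |
| 0.4 | 0.3 | 1.79 (0.839) | 1.73 (0.785) | 1.68 (0.755) | 1.60 (0.649) |
| 0.4 | 0.5 | 1.79 (0.836) | 1.73 (0.779) | 1.62 (0.673) | 1.49 (0.464) |
| 0.8 | 0.2 | 1.90 (0.870) | 1.83 (0.816) | 1.76 (0.771) | 1.61 (0.635) |
| 0.8 | 0.3 | 1.88 (0.856) | 1.79 (0.810) | 1.66 (0.711) | 1.48 (0.457) |
| 0.8 | 0.5 | 1.91 (0.849) | 1.72 (0.755) | 1.58 (0.554) | 1.28 (0.195) |

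The score stays in every fit; other covariates, clustering and backward elimination are not modelled. The unadjusted comparison of 0.63 with 0.75, at an assumed 248 per arm, has power 0.826 whatever f is.

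**4. Secondary outcomes.** With baseline as a covariate, the adjusted group difference is the raw difference minus β times the baseline difference between arms, where β is the within-arm slope. Late interviews create an expected baseline difference of f × d. At f = 0.5 and d = 0.2 to 0.5 that is 0.10 to 0.25 SD. If β is positive, an improvement is understated by β times that amount.

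**The case against.** The documents permit contamination but do not show that it happens. A reader might infer that many intervention patients would be interviewed after one or both sessions. Nothing supports that: the text sets no order either way, and following both sessions would need an interview later than 10 to 14 days after diagnosis. Booking a time may mean the same day, since E.3 plans onsite rooms, and the office-referral route puts consent and interview in one meeting. Some patients enrol on preoperative probability (E.1), so a session tied to diagnosis could fall well after enrolment. The mention in Protocol C of a recruiting interval between diagnosis and treatment describes the earlier cohort, so it does not date enrolment here.

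A reader might also infer that the trial's surgery comparison as a whole is compromised. It is not. The chi-square comparison of surgery by arm in SAP section 6 does not use these scores. In the GEE model, the forced baseline scores are unnamed, trust and communication are not labelled as baseline values, and terms not forced may be dropped.

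All of this limits the size of the point. It does not close the gap. The SAP describes the chi-square tests as preliminary and specifies the GEE model more fully. Elimination gives little protection, because a score that predicts surgery is the one likely to stay. If the trust and communication covariates are not enrolment values, they were measured later still, which is worse for adjustment.

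**Conclusion.** The point holds as an ordering gap. The schedule as written allows some intervention patients' enrolment communication, trust and SF-12 scores to be taken after CCE contact, with no counterpart in controls, and the SAP then places such scores beside the arm term. The bias in the adjusted effect on surgery is toward no effect if the session improves the score and the score predicts surgery.

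Its frequency and size cannot be computed from the documents. On the assumed inputs above, the loss ranges from slight (odds ratio 1.79 to 1.76 with a quarter of interviews late and a weak, small shift) to severe (1.91 to 1.28 with all late and a strong, larger shift). If the whole effect ran through the score and every interview were late, the adjusted effect would be zero by construction; that would follow from the assumption and is not evidence about this trial.

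Patient satisfaction is a firmer case of the same fault: it is in the surgery model but is listed only at 6 and 12 months, so it is measured after randomization whatever the timing of the first interview. The literacy score shares the timing gap but is less likely to change after one session.

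**What to change.** **Protocol E.2 and E.3.** State that the communication, trust and SF-12 blocks are completed at enrolment before the first CCE contact, with the same timing relative to consent in controls. The rest of the questionnaire may follow later, so the allowance for fatigue can stay. Record the date of each block and of the first CCE session.

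**SAP section 6.** Prespecify, without conditions that depend on trial conduct, that the primary arm comparison on surgery adjusts only for variables measured before CCE contact or not alterable by it, and excludes perceptions of communication, trust and patient satisfaction. Name the forced baseline scores. Label models containing the excluded scores exploratory.

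**Cost.** A sentence or two in the protocol, a reordered interview, a few date fields, a longer enrolment visit for some patients, and slightly less covariate adjustment. The order must be set before enrolment, because a missed pre-contact score cannot be recovered. One limit remains: with arm tied to recruitment dates, the research assistant giving the interview may still know the arm.
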